## 2.2 Hypotheses and/or Estimations

### Part A

The primary hypothesis is that tezepelumab effectively increases the probability of an IGA 0/1 response and an EASI 75 response at week 16 in subjects with moderate-to-severe AD.

**Specifically, the four primary hypotheses are as follows:**

#### **IGA 0/1 at week 16**

**H01: Odds ratio of IGA 0/1 at week 16 between tezepelumab 420 mg SC Q2W and placebo = 1**

**Vs.**

**H11: Odds ratio of IGA 0/1 at week 16 between tezepelumab 420 mg SC Q2W and placebo ≠ 1**

**H02: Odds ratio of IGA 0/1 at week 16 between tezepelumab 280 mg SC Q2W and placebo = 1**

**Vs.**

**H12: Odds ratio of IGA 0/1 at week 16 between tezepelumab 280 mg SC Q2W and placebo ≠ 1**

**EASI 75 at week 16**

**H03: Odds ratio of EASI 75 at week 16 between tezepelumab 420 mg SC Q2W and placebo = 1**

**Vs.**

**H13: Odds ratio of EASI 75 at week 16 between tezepelumab 420 mg SC Q2W and placebo ≠ 1**

**H04: Odds ratio of EASI 75 at week 16 between tezepelumab 280 mg SC Q2W and placebo = 1**

**Vs.**

**H14: Odds ratio of EASI 75 at week 16 between tezepelumab 280 mg SC Q2W and placebo ≠ 1**

An odds ratio greater than one indicates tezepelumab increases response compared to placebo.

**Family wise type I error rate will be strongly controlled at the 0.05 level (2-sided); the details of testing strategy are described in [Section 9.5.1](#).**

**Part B**

Part B is an estimation study; no hypotheses will be formally tested.

**3. Study Overview**

**3.1 Study Design**

This phase 2b study is designed to evaluate the safety and efficacy of tezepelumab as a monotherapy and explore its efficacy as adjunct therapy in subjects with moderate-to-severe AD. This study consists of Part A (the main **dose ranging** study evaluating tezepelumab as a monotherapy) and Part B (a **proof-of-concept** study evaluating tezepelumab as adjunctive therapy when combined with a TCS regimen). In Part A, two futility analyses are planned when approximately **the 80th and 160th subjects are projected to complete week 16**, respectively. Upon a result of “not futile” for the first

analysis and **Part A has completed enrollment of 240 subjects**, enrollment of subjects in Part B of the study will commence. A result of “futile” for either analysis in Part A will result in termination of both Part A and Part B of the study.

Eligible subjects for both Part A and Part B will include adults with a clinical diagnosis of AD at least 2 years prior to screening, with AD that affects  $\geq 10\%$  of body surface area as assessed by EASI, an IGA score of  $\geq 3$ , and an EASI score of  $\geq 16$ .

Part A and Part B of this study will consist of a 28-day screening period, a 52-week treatment period, and a **20-week** safety follow-up period. During the 28-day screening period, subjects must discontinue from all topical AD therapies, except for approved moisturizers (see Section 7.1.7 in the protocol), for at least the 7 consecutive days immediately prior to day 1. During the study, approved moisturizers are allowed to be applied, with the exception of 8 hours prior to any scheduled visit.

Part A is a dose-ranging, randomized, placebo-controlled, double-blind study designed to evaluate the safety and efficacy of tezepelumab as monotherapy in subjects with moderate-to-severe AD. Following the screening period, eligible subjects will be randomized 1:1:1:1 to receive 420 mg SC Q2W, 280 mg SC Q2W, 210 mg SC Q4W, or placebo. All subjects will receive a 420 mg SC loading dose (investigational product or placebo) as the first dose. Subjects will then receive the appropriate dose of investigational product at the week 2 visit, depending on which treatment group they are randomized to.

Depending on whether subjects are randomized to Q2W or Q4W dosing, the dose at week 2, **week 6, week 10 and so on**, could be placebo or tezepelumab. Non-responders are defined as those subjects who have not achieved at least a 50% improvement in EASI at week 16 compared to baseline (day 1). Subjects who are determined to be non-responders in Part A will receive tezepelumab 420 mg SC Q2W for the remainder of the study, beginning with the week 18 dose. The randomized treatment assignments for the non-responders will remain blinded until the end of study.

Part B is a randomized, placebo-controlled, double-blind **proof-of-concept** study designed to evaluate the safety and efficacy of tezepelumab when administered with moderate class TCS in adults with moderate-to-severe AD. Enrollment of subjects in Part B of the study will only commence if there is a result of “not futile” for the first interim analysis in Part A **and Part A has completed enrollment of 240 subjects**. Following the screening period, eligible subjects will be randomized 2:1 to receive 420 mg SC

Q2W or placebo; both groups in Part B will be allowed to use TCS after the day 1 visit. Non-responders in Part B will not be switched to 420 mg SC Q2W at week 18 and will remain on their initial dose for the duration of the study.

### 3.2 Sample Size

In Part A of this study, a total of 240 subjects will be randomized in a 1:1:1:1 ratio to tezepelumab 420 mg SC Q2W, 280 mg SC Q2W, 210 mg SC Q4W, and placebo (approximately 60 in each group). There is at least 85% power for each co-primary endpoint, assuming IGA 0/1 response rates of 10% and 40% for placebo and the highest tezepelumab dose group (420 mg SC Q2W), respectively, and assuming EASI response rates of 15% and 50%, respectively. These assumed treatment effects are based on results of other new agents (**recent biologic treatment**) in this indication ([\(DUPIXENT, 2017\)](#)). These calculations used a 2-sided  $\chi^2$  test at a significance level of 0.025 (to reflect the Bonferroni-based gatekeeping procedure described in [Section 9.5.1](#)) and assumed a 10% dropout rate.

Part B of this study is exploratory. A sample size of 60 subjects (40 in the tezepelumab 420 mg SC Q2W group and 20 in the placebo group) was chosen as an adequate sample size to provide initial evidence of tezepelumab as a promising agent for adjunct therapy. **The sample size of 60 in Part B was based on practical considerations rather than statistical considerations. For example, to observe treatment effect differences of tezepelumab 420 Q2W vs. placebo as 30% for IGA 0/1 and 35% for EASI 75 at week 16, the half-width of 95% CI will be approximately 20%.**

### 3.3 Adaptive Design

For Part A, two interim analyses are planned when approximately **the 80th and 160th subjects are projected to complete their week 16 assessments**, respectively. [REDACTED]

[REDACTED]

[REDACTED]

[REDACTED]

[REDACTED]. Further details are described in [Section 7.1](#) and **Supplemental SAP**.

## **4. Covariates and Subgroups**

### **4.1 Planned Covariates**

The analysis of the primary endpoints will be adjusted for the baseline covariate as follows:

- **Primary endpoint – IGA 0/1 at week 16:** Baseline IGA
- **Primary endpoint – EASI 75 at week 16:** Baseline EASI

### **4.2 Subgroups**

**Consistency of treatment effect across subgroups on the primary efficacy variables will be explored for Part A only. The following subgroup populations of interest in Part A will be included.**

Subgroup analyses are not planned for Part B.

## 5. Definitions

### 5.1 Safety Related Definitions

As detailed in [Section 3.1](#), subjects who are determined to be non-responders in Part A should switch to tezepelumab 420 mg SC Q2W for the remainder of the study, beginning with the week 18 dose.

#### Actual treatment received

##### *Part A:*

For Part A of the study, actual treatment will be defined as follows:

- If a subject either a) did not need to switch to tezepelumab 420 mg during the study, or b) should have switched to tezepelumab 420 mg but did not successfully do so, then the subject is considered a non-switcher. The subject's actual treatment received is defined below:
  - from day 1 until EOS for safety analysis of Day 1 to EOS (For safety analysis of Day 1 to week 16, use from day 1 until the day before the next dosing date after week 16 dose),
    - If a subject receives placebo only, the actual treatment will be defined as placebo
    - If a subject receives two or more doses of tezepelumab, the actual treatment will be defined as the highest dose of tezepelumab the subject receives since the date of the second IP (inclusive)
    - If a subject receives only one dose of tezepelumab, the actual treatment will be defined as the dose of tezepelumab the subject receives
- If a subject should have switched to tezepelumab 420 mg during the study and received a switching dose, then,
  - From day 1 until the day before the switch,
    - If a subject receives placebo only throughout this period, the actual treatment will be defined as placebo
    - If a subject receives two or more doses of tezepelumab during this period, the actual treatment will be defined as the highest dose of tezepelumab the subject receives since the date of the second IP (inclusive) until the day prior to the switch
    - If a subject receives only one dose of tezepelumab during this period, the actual treatment will be defined as the dose of tezepelumab the subject receives
  - From the date of switch until EOS,
    - If a subject receives at least one dose of tezepelumab 420 mg during this period, the actual treatment will be defined as tezepelumab 420 mg

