Part A is a dose-ranging, randomized, placebo-controlled, double-blind study designed to evaluate the safety and efficacy of tezepelumab as monotherapy in subjects with moderate-to-severe AD. Following the screening period, eligible subjects will be randomized 1:1:1:1 to receive 420 mg SC Q2W, 280 mg SC Q2W, 210 mg SC Q4W, or placebo. All subjects will receive a 420 mg SC dose (investigational product or placebo) as the first dose. Subjects will then receive the appropriate dose of investigational product at the week 2 visit, depending on which treatment group they are randomized to. Depending on if they are randomized to Q2W or Q4W dosing, the dose at week 2 could be placebo or tezepelumab. Non-responders are defined as those subjects who have not achieved at least a 50% improvement in EASI at week 16 compared to baseline (day 1). Subjects who are determined to be non-responders in Part A will receive tezepelumab 420 mg SC Q2W for the remainder of the study, beginning with the

week 18 dose. The randomized treatment assignments for the non-responders will remain blinded until the end of study.

Part B is a randomized, placebo-controlled, double-blind study designed to evaluate the safety and efficacy of tezepelumab when administered with moderate class TCS in adults with moderate-to-severe AD. Enrollment of subjects in Part B of the study will only commence if there is a result of “not futile” for the first interim analysis in Part A and Part A has completed enrollment of 240 patients. Following the screening period, eligible subjects will be randomized 2:1 to receive 420 mg SC Q2W or placebo; both groups in Part B will be allowed to use TCS after the day 1 visit. Non-responders in Part B will not be switched to 420 mg SC Q2W at week 18 and will remain on their initial dose for the duration of the study.

The overall study design is described by a study schema in [Section 2.1](#). The endpoints are defined in [Section 4.1](#).

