7.1 Treatment Procedures

7.1.1 Investigational Products

The amount of investigational product, total volume, quantity, dose start date/time, and box number are to be recorded on each subject's CRF.

Table 7-1. Study Treatments

Study Treatment Name	Amgen Investigational Product:^a	Placebo
Dosage Formulation	Each package will contain 3 vials.	Placebo will be presented in identical containers, and stored/packaged the same as tezepelumab.
Unit Dose Strength(s)/ Dosage Level(s) and Dosage Frequency	
Each subject will receive 3 injections per visit.
 
For subjects randomized to 420 mg SC Q2W, 280 mg SC Q2W, and 210 mg SC Q4W: volumes for injections from vials provided will be detailed in the Investigational Product Instruction Manual (IPIM).
 
Subjects randomized to Q4W dosing will receive placebo at intervening visits, such that all subjects receive an injection Q2W.
	
Each subject will receive 3 injections per visit.
 
For subjects randomized to placebo: volumes for injections from vials provided will be detailed in the IPIM.
 
Subjects will receive placebo dosing Q2W.

Route of Administration	SC injection	SC injection
Accountability	The amount of investigational product, total volume, quantity, dose start date/time, and box number of investigational product are to be recorded on each subject's CRF(s).	The amount of investigational product, total volume, quantity, dose start date/time, and box number of investigational product are to be recorded on each subject's CRF(s).
Dosing Instructions	
Investigational product will be administered by qualified study center personnel as the final activity for each study visit. The window for study visits is \pm 3 days.
 
Injection sites are to be rotated.
 
Subjects will be observed for 2 hours post-treatment at the day 1 and week 2 visits. For all other visits where investigational product is administered, subjects will be observed for a period of time at the discretion of the Investigator.
	
Investigational product will be administered by qualified study center personnel as the final activity for each study visit. The window for study visits is \pm 3 days.
 
Injection sites are to be rotated.
 
Subjects will be observed for 2 hours post-treatment at the day 1 and week 2 visits. For all other visits where investigational product is administered, subjects will be observed for a period of time at the discretion of the Investigator.

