7.1.5 Other Treatment Procedures

During the 28-day screening period, subjects must discontinue from all AD therapies, except for approved moisturizers (see [Section 7.1.7](#)), for at least the 7 consecutive days immediately prior to day 1. During the study, approved moisturizers are allowed to be applied, with the exception of 8 hours prior to any scheduled visit.

Medications and procedures permitted at any time during the study for subjects enrolled in Part A and Part B include:

- Basic skin care (cleansing and bathing), emollients, bleach baths, topical anesthetics, and antihistamines (all for any duration)
- Medications used to treat chronic diseases such as diabetes, hypertension, and asthma

Part A

In Part A of the study, if needed to control intolerable AD symptoms, rescue treatment for AD may be provided at the discretion of the investigator. Rescue is not allowed in the first 4 weeks of Part A. Topical calcineurin inhibitors may be used for rescue, but are to be reserved for problem areas only (eg, face, neck, intertriginous and genital areas). Investigators are to attempt to limit the first step of rescue therapy to topical medications, and escalate to systemic medications only for subjects who do not respond adequately following at least 7 days of topical treatment. If a subject receives rescue treatment with systemic corticosteroids or nonsteroidal systemic immunosuppressive drugs

(eg, cyclosporine, mycophenolate-mofetil, azathioprine), study treatment is to be immediately discontinued.

All subjects are to complete the schedule of study visits and assessments whether or not they complete study treatment or receive rescue treatment for AD.

Part A Rescue Guidance

Subjects who use TCS are to apply medium potency TCS once daily to areas with active lesions. Low potency TCS should be used once daily on areas of thin skin (eg, face, neck, intertriginous, genital areas, areas of skin atrophy) or for areas where continued treatment with medium potency TCS is considered unsafe.

Triamcinolone acetonide 0.1% cream or fluocinolone acetonide 0.025% ointment are recommended as medium potency TCS therapy; hydrocortisone 1% cream is recommended as low potency TCS therapy. After lesions are under control (clear or almost clear), subjects are to switch from medium potency to low potency TCS and treat once daily for 7 days, then cease TCS therapy.

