8.1 Discontinuation of Study Treatment

Subjects (or a legally acceptable representative) can decline to continue receiving investigational product and/or other protocol-required therapies or procedures at any

time during the study but continue participation in the study. If this occurs, the investigator is to discuss with the subject the appropriate processes for discontinuation from investigational product or other protocol-required therapies and must discuss with the subject the possibilities for continuation of the Schedule of Activities (see [Table 2-1](#) and [Table 2-2](#)) including different options of follow-up (eg, in person, by phone/mail, through family/friends, in correspondence/communication with other treating physicians, from the review of medical records) and collection of data, including endpoints, adverse events, disease-related events, and must document this decision in the subject's medical records. Subjects who receive systemic rescue therapies will be discontinued from study treatment but whenever safe and feasible, it is imperative that subjects remain on-study to ensure safety surveillance and/or collection of outcome data. Subjects who have discontinued investigational product and/or other protocol-required therapies or procedures should not be automatically removed from the study. Whenever safe and feasible, it is imperative that subjects remain on-study to ensure safety surveillance and/or collection of outcome data.

Subjects may be eligible for continued treatment with Amgen investigational product(s) and/or other protocol-required therapies by a separate protocol or as provided for by the local country's regulatory mechanism, based on parameters consistent with [Appendix 3](#).

Reasons for removal from protocol-required investigational product(s) or procedural assessments include any of the following:

- Decision by Sponsor
- Lost to follow-up
- Death
- Ineligibility determined
- Protocol deviation
- Non-compliance
- Adverse event
- Subject request
- Pregnancy

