10.2.1.2 Safety Analysis Set

The safety analysis set will consist of all randomized subjects who receive at least 1 dose of investigational product. Subjects will be analyzed according to the actual treatment received. The safety analyses described in [Section 10.3.2.3](#) will be based on the safety analysis set.

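### The one-dose rule for actual treatment puts correctly dosed 280 mg and 210 mg early stoppers in the 420 mg column of the Part A safety tables

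*SAP*

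**What the plan says.** Protocol Section 5.1 gives every Part A arm the same start: "All subjects will receive a 420 mg SC dose (investigational product or placebo) as the first dose". SAP Section 3.1 agrees and calls it a loading dose: "All subjects will receive a 420 mg SC loading dose (investigational product or placebo) as the first dose". In the 210 mg Q4W arm the week 2 injection is placebo, because "Subjects randomized to Q4W dosing will receive placebo at intervening visits, such that all subjects receive an injection Q2W" (Protocol Section 7.1.1, Table 7-1). The second active dose is therefore due at week 2 in the 280 mg arm and at week 4 in the 210 mg arm.

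SAP Section 5.1 defines actual treatment for Part A by the number of tezepelumab doses:

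- Two or more doses: "the actual treatment will be defined as the highest dose of tezepelumab the subject receives since the date of the second IP (inclusive"). The common first dose is left out.
- One dose: "If a subject receives only one dose of tezepelumab, the actual treatment will be defined as the dose of tezepelumab the subject receives". Nothing is left out.

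Both bullets appear for non-switchers and again for the pre-switch period of switchers. A subject who stops before any switching dose is a non-switcher.

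One dose of investigational product is enough to enter the safety set (SAP Section 6.2), and the Part A safety analyses are by actual treatment (SAP Sections 6.2 and 9.6). Protocol Section 10.2.1.2 sets the principle without defining it further: "Subjects will be analyzed according to the actual treatment received".

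**The concern.** The two adjacent rules treat the scheduled 420 mg first dose differently. With two or more doses it does not set the label; with one dose it is the label. Subjects who were given exactly what their arm prescribes then move into the top-dose column because they stopped early, with no dosing error. No text available for this review returns them to their arm. SAP Sections 6.3 to 6.6 are listed in the contents, but their text is not in the copy reviewed.

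Part A is a dose-ranging study, so its safety tables will be read across doses. Moving early stoppers from both lower doses into 420 mg can create a dose gradient or hide one. The most exposed table is adverse events leading to withdrawal of investigational product (SAP Section 9.6.1), because stopping for an adverse event is itself the event counted. Subjects who stop treatment are meant to stay on study (Protocol Section 8.1), and treatment-emergent events count up to the end-of-study date (SAP Section 5.1), so later events can follow them into the 420 mg column too.

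**Working it through.** **Step 1: apply the rule to correctly delivered doses.** The plan states no figure for one-dose subjects or for event rates, so there is none to reproduce. The label depends only on the last visit at which product was given:

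| Randomised arm | Day 1 only | Through week 2 | Through week 4 |
|---|---|---|---|
| 420 mg Q2W | 420 | 420 | 420 |
| 280 mg Q2W | **420** | 280 | 280 |
| 210 mg Q4W | **420** | **420** | 210 |

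The bold cells are the mislabelled subjects. The 210 mg arm is exposed for longer, through the week 2 placebo visit.

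**Step 2: denominators.** About 60 subjects per arm are planned (Protocol Section 10.1, SAP Section 3.2). With k280 and k210 one-dose stoppers in the two lower arms, the columns are 60+k280+k210, 60−k280 and 60−k210. For illustration take the same k in both: 60+2k, 60−k, 60−k. That gives 62/59/59 for k=1 and 64/58/58 for k=2. An extreme is k=6, where the whole assumed 10% dropout (6 of 60; timing not stated) falls at this point: 72/54/54.

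**Step 3: rates.** Let d subjects per arm have the event, the same in every arm, and let j of the k stoppers in each lower arm be among them.

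- 420 mg column: (d+2j)/(60+2k)
- Each lower-dose column: (d−j)/(60−k)
- True rate in every arm: d/60

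Setting (d+2j)/(60+2k) = d/60 gives j/k = d/60, and the lower-dose formula gives the same break-even. If the stoppers' rate j/k exceeds the arm's rate, 420 mg is raised and the lower doses are reduced. If it is below, the reverse happens.

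**Step 4: numbers, day 1 to week 16.** The values of d, k and j are assumptions; the rows run from no stopper with the event to all of them.

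| Event (true rate) | k | j | 420 mg | Each lower dose | Gap (points) |
|---|---|---|---|---|---|
| Withdrawal AE, d=6 (10%) | 1 | 0 | 6/62 = 9.7% | 6/59 = 10.2% | −0.5 |
| | 1 | 1 | 8/62 = 12.9% | 5/59 = 8.5% | +4.4 |
| | 2 | 0 | 6/64 = 9.4% | 6/58 = 10.3% | −1.0 |
| | 2 | 1 | 8/64 = 12.5% | 5/58 = 8.6% | +3.9 |
| | 2 | 2 | 10/64 = 15.6% | 4/58 = 6.9% | +8.7 |
| Withdrawal AE, d=3 (5%) | 1 | 0 | 3/62 = 4.8% | 3/59 = 5.1% | −0.2 |
| | 1 | 1 | 5/62 = 8.1% | 2/59 = 3.4% | +4.7 |
| | 2 | 0 | 3/64 = 4.7% | 3/58 = 5.2% | −0.5 |
| | 2 | 1 | 5/64 = 7.8% | 2/58 = 3.4% | +4.4 |
| | 2 | 2 | 7/64 = 10.9% | 1/58 = 1.7% | +9.2 |
| Any TEAE, d=18 (30%) | 1 | 0 | 18/62 = 29.0% | 18/59 = 30.5% | −1.5 |
| | 1 | 1 | 20/62 = 32.3% | 17/59 = 28.8% | +3.4 |
| | 2 | 0 | 18/64 = 28.1% | 18/58 = 31.0% | −2.9 |
| | 2 | 2 | 22/64 = 34.4% | 16/58 = 27.6% | +6.8 |
| Any TEAE, d=36 (60%) | 1 | 0 | 36/62 = 58.1% | 36/59 = 61.0% | −3.0 |
| | 1 | 1 | 38/62 = 61.3% | 35/59 = 59.3% | +2.0 |
| | 2 | 0 | 36/64 = 56.3% | 36/58 = 62.1% | −5.8 |
| | 2 | 2 | 40/64 = 62.5% | 34/58 = 58.6% | +3.9 |

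The true gap is zero in every row, so each gap shown comes from the label alone. Day 1 to end of study is not computed, because switchers carry a combined label there (SAP Section 9.6) and their number is not given.

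**The case against.** The strongest reply is that this is as-treated analysis taken literally. The subject received 420 mg and nothing else, the protocol asks for actual treatment, and an event after that single dose cannot be put down to a 280 mg or 210 mg dose never given. The SAP change log also shows that this definition was revised twice, which suggests a considered choice. The reply does not hold, because the neighbouring bullet already declines to let the scheduled first dose set the label, and that dose belongs to all three regimens. After one dose the three active arms have had the same exposure, so the 420 mg label says nothing about regimen; it only pools these subjects in the top-dose column.

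The points on size mostly stand. The number of one-dose stoppers is unknown and may be zero. One route is closed early: "Rescue is not allowed in the first 4 weeks of Part A" (Protocol Section 7.1.5), so the mandatory stop after systemic rescue should not produce them. Reasons for stopping other than adverse events (Protocol Section 8.1: "Reasons for removal from protocol-required investigational product(s) or procedural assessments include any of the following", among them subject request and non-compliance) can push the shift the other way. The gaps are often within chance variation: the standard error of a 60-versus-60 difference, √(2p(1−p)/60), is 4.0 points at 5%, 5.5 at 10%, 8.4 at 30% and 8.9 at 60%. At k=1 only the 5% case (+4.7) exceeds it. The largest gap, +9.2, needs two of the three withdrawals in each lower arm to follow exactly one active dose.

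Two narrower points also stand. Equal k is only illustrative, since the 210 mg arm has the longer window. The pre-switch one-dose bullet is almost empty for these subjects, who would normally have several active doses before a week 18 switch.

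Disposition by randomised group, with reasons for stopping (SAP Section 9.2), shows early stoppers by arm. It does not return their adverse events to that arm.

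**Conclusion.** The concern holds. As written, the one-dose rule places correctly dosed 280 mg and 210 mg subjects under 420 mg, and for any k above zero the denominators are shifted. The direction and size of the shift in rates are conditional. With equal true rates and k of 1 or 2 per lower arm, the spurious gap between 420 mg and a lower dose runs from −1.0 to +9.2 points for adverse events leading to withdrawal (true 5% or 10%), and from −5.8 to +6.8 points for any treatment-emergent event (true 30% or 60%). These ranges rest on assumed values of k, j and d and on equal k in the two lower arms; with k=0 there is no effect. The mechanism is certain from the text available, while its practical size is not known. The effect is confined to descriptive Part A safety tables. It should be fixed, because it is an avoidable artefact in a dose comparison that the study is designed to make.

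**What to change.** In the one-dose bullet of SAP Section 5.1, Part A, write: *If a subject randomised to tezepelumab received, as the only tezepelumab dose, the scheduled day 1 first dose, and any later investigational product was given as randomised, actual treatment is the randomised treatment; otherwise it is the dose received.* State that a missed administration is not a dosing error for this purpose. Use the same wording in the pre-switch branch for consistency, although few if any subjects will fall there. Misdosed subjects, including a placebo subject given tezepelumab in error, keep the dose-received label.

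Footnote the Part A safety tables with the number of such subjects per arm, and say that this is how actual treatment in Protocol Section 10.2.1.2 is read.

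The cost is a short SAP edit, one derivation line and one footnote. The one drawback is that for these subjects the label shows the assigned regimen and not the single dose given, which the footnote discloses. The change affects an analysis label only; no dosing or treatment rule is touched.
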